#### 14.6. **APPENDIX F: ADMINISTRATION OF PEMBROLIZUMAB**

Administration of pembrolizumab will be witnessed by the investigator and/or site staff. The total volume of study treatment infused will be compared to the total volume prepared to determine compliance with each dose administered.

On day 1 of every cycle subjects will receive a 200 mg flat dose of pembrolizumab on an every-3-week schedule; this is 2 vials of 100 mg/4mL per infusion. Intrasubject dose escalation of pembrolizumab is not permitted.

Formulation and administration instructions for pembrolizumab are provided below.

- Pembrolizumab infusion solutions should be prepared in 0.9% Sodium Chloride Injection, USP (normal saline) or 5% Dextrose Injection, USP (5% dextrose) and the final concentration of Pembrolizumab in the infusion solutions should be between 1.0 mg/mL and 10.0 mg/mL.
- Pembrolizumab SHOULD NOT BE MIXED WITH OTHER RECONSTITUTION DILUENTS.
- Parenteral drug products should be inspected visually for particulate matter and discoloration prior to administration. Discard the drug product vial if extraneous particulate matter other than translucent to white proteinaceous particles are observed.
- Do not use Pembrolizumab if discoloration is observed.
- DO NOT SHAKE OR FREEZE THE VIAL(S).
- DO NOT ADMINISTER THE PRODUCT AS AN [INTRAVENOUS (IV) PUSH OR BOLUS].
- DO NOT COMBINE, DILUTE OR ADMINISTER THE PRODUCT AS AN INFUSION WITH OTHER MEDICINAL PRODUCTS.

##### *Preparation of Infusion Solution*

- Aseptic technique must be strictly observed throughout the preparation procedure preferably in a biologic safety cabinet or hood since no anti-microbial preservative is present in the solutions.

- Equilibrate required number of Pembrolizumab vials to room temperature
- Choose a suitable infusion bag size so that the following conditions are met:
  - Concentration of Pembrolizumab is between 1.0 mg/mL and 10.0 mg/mL
  - The infusion volume to bag capacity ratio should not be less than 0.3. In other words, the bag must be filled to at least 30% of its capacity.
- Choose a suitable infusion bag material. The bag may be empty or it may contain normal saline. The following infusion bag materials are compatible with Pembrolizumab:
  - PVC plasticized with DEHP
  - Non-PVC (polyolefin)
  - EVA
  - PE lined polyolefin

\*Contact Sponsor for materials not listed above

- Calculate the volume of Pembrolizumab and normal saline required to prepare the infusion (admixture) bag

Volume of Pembrolizumab (mL) = required dose amount (mg) / 25.0 (mg/mL)

Volume of normal saline = total infusion volume – volume of Pembrolizumab from above

- If a bag pre-filled with normal saline is being used, remove the excess volume of normal saline using a sterile syringe (Polypropylene, latex-free) attached to a suitable needle. Keep in consideration the excess bag fill volume as well as the volume of reconstituted Pembrolizumab to be added to the bag to prepare the infusion solution.
- If an empty bag is being used, withdraw the necessary volume of normal saline from another appropriate bag and inject into the empty bag. Keep in consideration the volume of reconstituted Pembrolizumab to be added to the bag to prepare the infusion solution.

- Withdraw the required volume of Pembrolizumab from the vial(s) (up to 4 mL from each vial) using a sterile syringe attached to a suitable needle. The vial(s) may need to be inverted to remove solution.

$$\text{Volume of Pembrolizumab (mL)} = \text{required dose amount (mg)} / 25.0 \text{ (mg/mL)}$$

Note: If it is necessary to use several vials, it is advisable to withdraw from several vials into a suitable size single use syringe using a new needle for each vial.

- Add the required Pembrolizumab into the infusion IV bag containing normal saline and gently invert the bag 10-15 times to mix the solution.

### *Infusion Instructions*

- Pembrolizumab infusions should be administered over a period of 30 minutes, with a window of -5 and +10 minutes, using an infusion pump. A central catheter is not required for infusion; however if a subject has a central venous catheter in place, it is recommended that it be used for the infusion.

The following infusion set materials are compatible with Pembrolizumab:

- PVC Infusion set that is plasticized using DEHP
- PVC and tri-(2-ethylhexyl) trimellitate (TOTM) infusion set
- Polyethylene lined PVC infusion set
- PVC Infusion set that is plasticized using Di-2-ethylhexyl Terephthalate (DEHT)
- Polyurethane set
- A sterile, non-pyrogenic, low-protein binding 0.2 to 5  $\mu\text{m}$  in-line-filter made of polyethersulfone (PES) must be used during administration to remove any adventitious particles. If the infusion set does not contain 0.2 to 5  $\mu\text{m}$  in-line filter, it is recommended to use 0.2 to 5  $\mu\text{m}$  add-on filter which may contain an extension line (Note: the materials of the extension line and filter should be as mentioned above).
- Attach the infusion line to the pump and prime the line, either with normal saline (at least 25 mL) or with infusion solution as per local SOP, before starting the infusion.

- Infuse Pembrolizumab over approximately 30 minutes, with a window of -5 and +10 minutes, through a peripheral line or indwelling catheter.
  - Whenever possible, the lowest infusion rate should be used that will allow completion of the infusion within the 30 minutes
  - Maximum rate of infusion should not exceed 6.7 mL/min. through a peripheral line or indwelling catheter. However, when it is necessary to infuse a larger volume (i.e. 250 mL), the flow rate may go as high as 10 mL/mL (maximum) in order to keep the infusion within the window as defined above.
- Use 30 mL normal saline to flush the infusion line at the end of infusion. If institutional guidelines do not allow the flushing of the infusion line at the completions of the infusion, please prepare excess volume of drug/diluent admixture solution that is required to make up for the volume of the dosing solution lost in the infusion line. For example if a subject is receiving 100 mL IV infusion and it is known that 18mL will be left in the infusion line since the line is not flushed, the pharmacist should prepare 118 mL of drug/diluent admixture solution in a 200 mL bag to make sure that the 100 mL will be delivered to the subject.
- DO NOT CO-ADMINISTER OTHER DRUGS THROUGH THE SAME INFUSION LINE.
- UNUSED INFUSION SOLUTION FOR INJECTION SHOULD NOT BE USED FOR ANOTHER INFUSION OF THE SAME SUBJECT OR DIFFERENT SUBJECT.
- Discard any unused portion left in the vial, as the product contains no preservative.

14.7. **APPENDIX G: TEMPERATURE AND LIGHT EXCURSION FORM FOR EPACADOSTAT**

**1. To be filled out by INVESTIGATIONAL CENTER STAFF:**

In the event of temperature excursion during storage of study drug at your investigational center, please complete all fields  
**INCB024360 bottles:** Store at room temperature (15-30°C)  
**MK-3475 vials:** Store between 2-8 Degrees Celsius ( Reconstituted if not used immediately should be stored between 2-8 Degrees Celsius up to 20 hours and allowed to equilibrate to room temperature prior to subsequent use. MK-3475 solutions may be stored at room temperature for a cumulative time of up to 4 hours. This includes room temperature storage of reconstituted or liquid MK-3475 solution in vials, room temperature storage of infusion solution in the IV bag and the duration of infusion.

Site number: \_\_\_\_\_  
Principal Investigator: \_\_\_\_\_

Affected (Please select one)	Lot-Number	Retest/Expiry date	No. of Container
INCB024360 			
MK-3475 			

Date of temperature excursion / alarm: \_\_\_\_\_  
Date excursion / alarm detected: \_\_\_\_\_  
Length of excursion (HH:MM): \_\_\_\_\_  
Min/Max temperature recorded: \_\_\_\_\_

Please provide information about the cause of the temperature excursion - tick the appropriate box (es):

 Hot weather ( temperature excursion above 30 Degrees Celsius for INCB024360 /above 8 Degrees Celsius for MK-3475)	 Was not protected from light or humidity
 Cold weather (temperature excursion below 15 Degrees Celsius for INCB024360/ and below 2 Degrees Celsius for MK-3475)	 Other
 Temperature log misplaced / moved/not monitored	 Unknown

Please provide specific detail about the temperature excursion (Please attach copies of temperature monitor logs/graphs, etc. when available): \_\_\_\_\_

**Site Email address to return response:** \_\_\_\_\_

If no EMAIL available please provide FAX Number: \_\_\_\_\_

Were any of the affected containers dispensed to or administered to study subjects:  Yes  No	Please specify NEXT PATIENT VISIT DATE (dd/mmm/yyyy): _____
---	---

Site representative Name/Role: (BLOCK LETTERS)	Signature	Date (DD-MMM-YYYY)
---	-----------	-----------------------

## 14.8. APPENDIX H: DEFINITION OF irRC

### 14.8.1. Definition of Tumor Response Using irRC

The sum of the products of diameters at tumor assessment using the irRC for progressive disease incorporates the contribution of new measurable lesions. Each net percentage change in tumor burden per assessment using irRC criteria accounts for the size and growth kinetics of both old and new lesions as they appear.

### 14.8.2. Definition of Index Lesions Response Using irRC

- **irComplete Response (irCR):** Complete disappearance of all index lesions. This category encompasses exactly the same subjects as “CR” by the mWHO criteria.
- **irPartial Response (irPR):** Decrease, relative to baseline, of 50% or greater in the sum of the products of the two largest perpendicular diameters of all index and all new measurable lesions (i.e., percentage change in tumor burden). Note: the appearance of new measurable lesions is factored into the overall tumor burden, but does not automatically qualify as progressive disease until the SPD increases by  $\geq 25\%$  when compared to SPD at nadir.
- **irStable Disease (irSD):** Does not meet criteria for irCR or irPR, in the absence of progressive disease.
- **irProgressive Disease (irPD):** At least 25% increase percentage change in tumor burden (i.e., taking sum of the products of all index lesions and any new lesions) when compared to SPD at nadir.

### 14.8.3. Definition of Non-Index Lesions Response Using irRC

- **irComplete Response (irCR):** Complete disappearance of all non-index lesions. This category encompasses exactly the same subjects as “CR” by the mWHO criteria.
- **irPartial Response (irPR) or irStable Disease (irSD):** non-index lesion(s) are not considered in the definition of PR, these terms do not apply.
- **irProgressive Disease (irPD):** Increases in number or size of non-index lesion(s) does not constitute progressive disease unless/until the percentage change in tumor burden increases by 25% (i.e., the SPD at nadir of the index lesions increases by the required amount).

### 14.8.4. Impact of New Lesions on irRC

New lesions in and by themselves do not qualify as progressive disease. However their contribution to total tumor burden is included in the SPD which in turn feeds into the irRC

criteria for tumor response. Therefore, new non-measurable lesions will not discontinue any subject from the study.

#### 14.8.5. **Definition of Overall Response Using irRC**

Overall response using irRC will be based on these criteria:

- **Immune-Related Complete Response (irCR):** Complete disappearance of *all* tumor lesions (index and nonindex together with no new measurable/unmeasurable lesions) for at least 6 weeks from the date of documentation of complete response.
- **Immune-Related Partial Response (irPR):** The sum of the products of the two largest perpendicular diameters of all index lesions is measured and captured as the SPD baseline. At each subsequent tumor assessment, the sum of the products of the two largest perpendicular diameters of all index lesions and of new measurable lesions are added together to provide the Immune Response Sum of Product Diameters (irSPD). A decrease, relative to baseline of the irSPD compared to the previous SPD baseline, of 50% or greater is considered an irPR.
- **Immune-Related Stable Disease (irSD):** irSD is defined as the failure to meet criteria for immune complete response or immune partial response, in the absence of progressive disease.
- **Immune-Related Progressive Disease (irPD):** It is recommended in difficult cases to confirm PD by serial imaging. Any of the following will constitute progressive disease:
  - At least 25% increase in the sum of the products of all index lesions over baseline SPD calculated for the index lesions.
  - At least a 25% increase in the sum of the products of all index lesions and new measurable lesions (irSPD) over the baseline SPD calculated for the index lesions.

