### **1.2. Secondary Objectives**

- 1.2.1. To evaluate objective response rate (RR) by RECIST v1.1 and irRC
- 1.2.2. To evaluate overall survival (OS)
- 1.2.3. To assess the safety and tolerability of epacadostat in combination with pembrolizumab by NCI CTCAE v5

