#### 14.8.6. Immune-Related Response Criteria Definitions

Index Lesion Definition	Non-Index Lesion Definition	New Measurable Lesions	New Unmeasurable Lesions	Percent change in tumor burden (including measurable new lesions when present)	Overall irRC Response
Complete Response	Complete Response	No	No	-100%	irCR
Partial Response	Any	Any	Any	$\geq -50\%$	irPR
				$< -50\%$ to $< +25\%$	irSD
				$> +25\%$	irPD
Stable Disease	Any	Any	Any	$< -50\%$ to $< +25\%$	irSD
				$> +25\%$	irPD
Progressive Disease	Any	Any	Any	$\geq +25\%$	irPD

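### Appendix H measures irRC progression from the SPD nadir in 14.8.2 and 14.8.3 but from baseline SPD in 14.8.5, so one scan can fall into two categories

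*Combined protocol and SAP*

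**What the plan says.** Combined protocol and SAP, Appendix H:

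- **14.8.2 (index lesions).** irPD is a rise of at least 25% in tumour burden, "taking sum of the products of all index lesions and any new lesions) when compared to SPD at nadir". The note attached to irPR in the same section repeats the nadir reference.
- **14.8.3 (non-index lesions).** Growth of these lesions is not progression until "the SPD at nadir of the index lesions increases by the required amount".
- **14.8.5 (overall response).** Two irPD criteria are given, and either suffices. The first is "At least 25% increase in the sum of the products of all index lesions over baseline SPD calculated for the index lesions". The second applies the same 25% to index lesions plus "new measurable lesions (irSPD) over the baseline SPD calculated for the index lesions".
- **14.8.5, the other categories.** For irPR: "A decrease, relative to baseline of the irSPD compared to the previous SPD baseline, of 50% or greater is considered an irPR". For stable disease: "irSD is defined as the failure to meet criteria for immune complete response or immune partial response, in the absence of progressive disease".
- **14.8.6 (summary table).** One percent-change column carries the −100%, −50% and +25% cut-offs. It does not say what the change is measured from.

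The scale matters to a named objective. Section 1.2.1 reads "To evaluate objective response rate (RR) by RECIST v1.1 and irRC". Section 14.8.7 requires an irPR to be confirmed by a second evaluation that meets the response criteria.

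**The concern.** Both 14.8.2 and the second criterion in 14.8.5 count index lesions together with new lesions. They are therefore not a lesion-level rule standing beside a patient-level rule: they set two reference points for essentially the same quantity. The two agree only when the tumour never shrank below baseline. Once it has shrunk, the nadir rule calls progression earlier than the baseline rule, and two assessors who each follow the protocol can record different categories for one scan.

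At stake is the reproducibility of irPD calls and, in one narrow situation, whether a patient counts as a confirmed irRC responder. In an open-label, single-arm trial, a reference chosen after the data are seen would be an unplanned analysis decision.

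**Working it through.** The plan states no figure that depends on this definition, so there is nothing of its own to reproduce. Sample size and power rest on 6-month PFS, which section 12.2.1 assesses by RECIST v1.1.

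**Inputs.** B = baseline SPD, N = nadir SPD, C = current SPD, counting new measurable lesions where present. B is set to 100 for illustration; N and C are illustrative values, not trial data.

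**Rules.**
- Nadir rule (14.8.2, 14.8.3): irPD if C ≥ 1.25 × N.
- Baseline rule (14.8.5): irPD if C ≥ 1.25 × B.
- irPR (14.8.2 and 14.8.5 alike): C ≤ 0.50 × B.
- irSD: the remainder, leaving irCR aside.

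**Where they disagree.** Whenever 1.25 × N ≤ C < 1.25 × B. With B = 100 the upper limit is 125. The lower limit is 1.25 × 80 = 100 for N = 80, 1.25 × 60 = 75 for N = 60, 1.25 × 40 = 50 for N = 40, and 1.25 × 30 = 37.5 for N = 30.

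**Examples (B = 100).**

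| N | C | Change from nadir | Change from baseline | Nadir rule | Baseline rule |
|---|---|---|---|---|---|
| 100 | 125 | +25% | +25% | irPD | irPD |
| 100 | 124 | +24% | +24% | irSD | irSD |
| 80 | 100 | 100/80 − 1 = +25% | 0% | irPD | irSD |
| 60 | 80 | 80/60 − 1 = +33.3% | −20% | irPD | irSD |
| 40 | 60 | 60/40 − 1 = +50% | −40% | irPD | irSD |
| 30 | 40 | 40/30 − 1 = +33.3% | −60% | irPD | irPR |

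In the last row the scan meets the irPR cut-off whichever progression rule is used. Under the nadir rule it also meets irPD, and the text does not say which category wins.

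**When the irRC response rate can change.** irPR is measured from baseline in both sections, so a first response is identified the same way. The conflict reaches the response count only through confirmation, when the second scan satisfies 1.25 × N ≤ C ≤ 0.50 × B. That requires N ≤ 0.50/1.25 × B = 0.40 × B. For N = 30 the range is 37.5 to 50. Take a first response at 30 and a confirmatory scan at 40: the baseline rule confirms the irPR, while the nadir rule leaves confirmation undetermined. By contrast, a first response at 40 followed by 60 fails confirmation under both rules, because 60 is only 40% below baseline.

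**Size per patient.** With 30 enrolled (section 12.4), one reclassified patient moves the rate by 1/30 = 3.3 percentage points, or slightly more if the evaluable denominator is below 30. The documents do not allow the number of such patients to be estimated.

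**The case against.** The strongest reply is that almost nothing the plan will report depends on irPD. Section 10.1 makes RECIST v1.1 the primary measure of tumour response. PFS (12.2.1), response rate (12.3 and Table 8) and duration of response (12.3) are all by RECIST v1.1. The best irRC response in 14.8.7 takes in all assessments up to subsequent therapy and is not cut off at irPD, so a confirmed responder stays a responder whichever rule later calls progression. All of that stands, and it limits the point.

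A reader might infer that the baseline rule inflates immune-related disease control or duration of response. The documents do not support that, because no irRC disease-control or irRC duration endpoint is planned. A reader might also take the gap between the two thresholds as an estimate of delayed progression. With baseline 100 and nadir 40 they are 125 and 50, a ratio of 2.5. That ratio is simply baseline divided by nadir for the chosen numbers and varies by patient. Nor is the conflict confined to responders: the nadir 80, current 100 case never reached irPR.

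It can also be argued that 14.8.5 governs because it assigns overall response. The text does not say so. Section 10.2.3 does not settle the matter in favour of nadir either: its smallest-sum reference belongs to the target-lesion criteria, with a 20% threshold.

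What survives is the contradiction itself, in current text, with no stated precedence.

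**Conclusion.** The inconsistency is real but limited. Any patient whose SPD drops below baseline and then regrows into the range from 1.25 × nadir up to, but not including, 1.25 × baseline has two irRC categories under the protocol: irPD, and either irSD or irPR. The consequences are ambiguous irPD calls and, for objective 1.2.1, ambiguous confirmation of an irPR when the second scan is still at least 50% below baseline but at least 25% above nadir. Each patient in that situation is worth at least 3.3 percentage points of the irRC response rate. The primary endpoint, duration of response, RECIST response rate, sample size and power are unaffected.

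This rests on reading the 25% and 50% cut-offs as written and on no section having precedence. It should be corrected before analysis, but it does not threaten the trial's main conclusion.

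**What to change.** Reconcile 14.8.2, 14.8.3, 14.8.5 and 14.8.6 to one stated irPD reference before analysis.

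- Nadir has the most support within the appendix (twice in 14.8.2, once in 14.8.3). If it is adopted, say whether it is the nadir of the index-lesion SPD or of the irSPD including new measurable lesions. Section 14.8.3 speaks of index lesions only, whereas 14.8.2 includes new lesions.
- In 14.8.6, label the references separately. The irPR cut-off (−50%) stays relative to baseline, as 14.8.2 and 14.8.5 both have it; only the irPD cut-off (+25%) takes the reconciled reference. A single nadir reference for the whole column would wrongly shift the irPR threshold.
- State which category is recorded when a scan meets both irPR and irPD, so that confirmation under 14.8.7 is determined.

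The study calendar footnotes and section 10.3 mention irRC alongside RECIST v1.1 when progression is confirmed. Where irPD also informs whether treatment continues, the request is only that the passages be reconciled.

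The cost is a few lines of appendix wording. No change is needed to data collection, sample size or the primary analysis.

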#### 14.8.6. Immune-Related Response Criteria Definitions

Index Lesion Definition	Non-Index Lesion Definition	New Measurable Lesions	New Unmeasurable Lesions	Percent change in tumor burden (including measurable new lesions when present)	Overall irRC Response
Complete Response	Complete Response	No	No	-100%	irCR
Partial Response	Any	Any	Any	$\geq -50\%$	irPR
				$< -50\%$ to $< +25\%$	irSD
				$> +25\%$	irPD
Stable Disease	Any	Any	Any	$< -50\%$ to $< +25\%$	irSD
				$> +25\%$	irPD
Progressive Disease	Any	Any	Any	$\geq +25\%$	irPD

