### 12.3. Secondary Analyses

Secondary efficacy analysis will be conducted for the efficacy evaluable population. Secondary endpoints and analyses are as follows:

To evaluate response rate (RR). Response will be determined by RECIST v1.1 for solid tumors. The 95% exact CI for the RR will be estimated using the Clopper-Pearson method. For objective responders, the duration of response is the time from the first objective response contributing to an objective response, to the first objective response of PD (by RECIST v1.1) occurring after the first objective response contributing to the objective response.

To evaluate overall survival (OS). Time-to-event data will be analyzed by the Kaplan-Meier method, treating subjects with no observed death or progression as censored at their last date known to be alive. For the OS analysis, the nonparametric Kaplan-Meier method will be used to estimate the survival time distribution and the median survival.

To assess the safety and tolerability of epacadostat in combination with pembrolizumab. AEs will be coded by the MedDRA, and incidences will be tabulated by preferred term and system organ class for all events, related events, and events  $\geq$  Grade 3. Severity of AEs will be based on the CTCAE v5 scale as indicated. Quantitative safety variables and their changes from baseline (laboratory, vital signs) will be summarized with descriptive statistics. Clinically significant abnormal values will be flagged and tabulated based on predefined criteria. Exposure will be analyzed by describing dose intensity, which is defined as the dose-received divided by the dose planned over a given time interval. This will be done by cycle as well as overall cycles received for epacadostat and pembrolizumab. For each cycle, incidences of dose reductions and cycle

delays will also be tabulated, by reason for the reduction or delay. The percentage of subjects with any delay and/or reduction will also be calculated.

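### The cut-offs printed in the irRC table (14.8.6) do not match the irRC definitions in 14.8.2 and 14.8.5, whichever way the signs are read

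*Combined protocol and SAP*

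**What the plan says.** Secondary objective 1.2.1 is "To evaluate objective response rate (RR) by RECIST v1.1 and irRC". Appendix H (14.8) supplies the irRC rules, in words and then in a table.

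**In words.** For index lesions, 14.8.2 defines irPR as "Decrease, relative to baseline, of 50% or greater in the sum of the products of the two largest perpendicular diameters", counting index and new measurable lesions, and irPD as "At least 25% increase percentage change in tumor burden". For overall response, 14.8.5 says: "A decrease, relative to baseline of the irSPD compared to the previous SPD baseline, of 50% or greater is considered an irPR". It adds that "irSD is defined as the failure to meet criteria for immune complete response or immune partial response, in the absence of progressive disease", and it counts as progression "At least a 25% increase in the sum of the products of all index lesions and new measurable lesions (irSPD") over baseline.

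**In the table.** Section 14.8.6 is entered by index-lesion status, and the overall category is then read from a signed column headed "Percent change in tumor burden (including measurable new lesions when present"):

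| Index row | irPR | irSD | irPD |
|---|---|---|---|
| Partial Response | `≥ -50%` | `< -50% to < +25%` | `> +25%` |
| Stable Disease | not offered | `< -50% to < +25%` | `> +25%` |
| Progressive Disease | not offered | not offered | `≥ +25%` |

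A separate Complete Response row gives irCR at -100%.

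**In the analysis.** Section 12.3 plans the response rate on one criterion only: "Response will be determined by RECIST v1.1 for solid tumors". Table 8 does the same.

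**The concern.** The table restates the rule that 14.8.5 gives in words, and the two disagree. On a signed scale a decrease of at least 50% is a change of -50% or lower, so the irPR sign points the wrong way and so does the lower limit of irSD. Separately, the Partial Response and Stable Disease rows start irPD strictly above +25%, while the prose and the Progressive Disease row include +25%.

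This matters because 14.8.6 is the only place that combines index lesions, non-index lesions and new lesions into an overall irRC category in tabular form. That makes it the natural source for a site worksheet or a derivation program. The best overall irRC response in 14.8.7 is then built from those overall responses. The documents contain no statement that the prose prevails over the table.

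**Working it through.** The plan states no figure on this point, so there is none to reproduce. The check applies both sets of rules to the same values.

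**Inputs.** Let x be the signed percentage change in total burden.

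- Prose (14.8.2, 14.8.5): irPR if x ≤ -50; irPD if x ≥ +25; irSD if -50 < x < +25.
- Table (14.8.6): the cells set out above.

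**Three readings of the table.**

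- A, literal: irPR if x ≥ -50. irSD must satisfy both printed inequalities, x < -50 and x < +25, which reduces to x < -50.
- B, mixed: the irSD cell is the interval -50 < x < +25, and the irPR cell stays literal.
- C, shorthand: `≥ -50%` means a decrease of at least 50%, so x ≤ -50, and irSD is the interval.

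All three take irPD as x > +25 in the Partial Response (PR) and Stable Disease (SD) rows.

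**Results.**

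| x | Prose | A, PR row | A, SD row | B, PR row | B, SD row | C, PR row | C, SD row |
|---|---|---|---|---|---|---|---|
| -60% | irPR | irSD | irSD | none | none | irPR | none |
| -50% | irPR | irPR | none | irPR | none | irPR | none |
| -30% | irSD | irPR | none | irPR and irSD | irSD | irSD | irSD |
| +24% | irSD | irPR | none | irPR and irSD | irSD | irSD | irSD |
| +25% | irPD | irPR | none | irPR | none | none | none |
| +26% | irPD | irPR and irPD | irPD | irPR and irPD | irPD | irPD | irPD |

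The SD-row entries at -50% and below have no practical weight. If the first column refers to index lesions alone, an SD-row patient's index burden has fallen by less than 50%, and new lesions can only add to the total.

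**Count over whole percentages from -99 to +100** (49 + 1 + 74 + 1 + 75 = 200 values), PR row:

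- A: the 49 values from -99 to -51 move from irPR to irSD; -50 stays irPR; the 74 values from -49 to +24 move from irSD to irPR; +25 becomes irPR; the 75 values above +25 satisfy irPR and irPD together.
- B: the same 49 values have no category, and the same 74 are both irPR and irSD.
- C: all values agree with the prose except +25, which has no category.

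In the SD row, A leaves every value from -50 to +25 without a category. C leaves +25 without one.

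No reading gives irPD at exactly +25% in these two rows, so no reading matches the prose throughout.

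**After correction.** With irPR at x ≤ -50, irSD at -50 < x < +25 and irPD at x ≥ +25, each value in the PR row gets one category, the prose one: -60 irPR, -50 irPR, -49 irSD, 0 irSD, +24 irSD, +25 irPD.

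**The case against.** The best defence is that nobody need be misled. Section 14.8.5 presents its own list as the basis for overall response, states the thresholds correctly in words, and agrees on the size of the thresholds with 14.8.2. No planned analysis is tied to the table: section 12.2.1 bases PFS on RECIST v1.1, section 12.3 and Table 8 base the response rate on it, and section 10.1 makes it the primary response measure. Inequality signs are also easily altered when a table is converted from PDF. All of this stands. It limits the consequence, but it leaves a table that contradicts its own definitions.

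Two stronger readings are tempting, and the documents do not support either.

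- A reader might infer that irPR and irSD change places for every patient. They do not. Only the index Partial Response row offers irPR. A patient with stable index lesions and a 30% fall enters the Stable Disease row and, read literally, gets no category. Even in the Partial Response row, a total change above -50% arises only if the first column means index lesions alone, with new lesions added afterwards. The wording of 14.8.2 already counts new measurable lesions. The table's own irSD and irPD cells in that row make sense only on the index-only reading.
- A reader might take the 22% partial response and 14% stable disease in section 2.1 and infer that the response rate would become 14%. Those are centrally reviewed RECIST v1.1 figures, not irRC categories, and Stable Disease row patients cannot become irPR.

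Nor do the reversal and the unclassified +25% occur together in the Partial Response row. Under the literal reading +25% falls into irPR there. It is unclassified in both rows only under the shorthand reading, which reverses nothing. Under that reading the +25% gap concerns irSD against irPD at a single value and cannot change a response rate.

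**Conclusion.** The point holds as an internal contradiction of low severity. The cells of 14.8.6, as printed, conflict with 14.8.2 and 14.8.5 under each of the three readings.

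The size depends on the reading. Under the shorthand reading the effect is confined to a change of exactly +25%. Under the literal reading, Partial Response row patients with decreases greater than 50% drop out of the irRC response rate, and any in that row whose total burden changed by more than -50% (a smaller fall, or a rise) enter it. The documents give no expected distribution of irRC changes, so the net error cannot be calculated. With a denominator of at most the 30 planned patients, each misclassified patient moves the rate by at least 1/30 = 3.3 percentage points.

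Only the irRC part of objective 1.2.1 is exposed. Primary 6-month PFS and the section 12.3 response rate are unaffected. The conclusion assumes that the signs in the source table are as printed here.

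**What to change.** First check the inequality signs in 14.8.6 against the source table. If they stand as printed, replace the cells as follows, in every row where the category applies:

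- irPR: change ≤ -50%
- irSD: change > -50% and < +25%
- irPD: change ≥ +25%

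The Stable Disease row then needs only the irSD and irPD cells. One sentence stating that 14.8.5 governs if table and text differ would protect against any remaining ambiguity.

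In the same edit, reconcile the reference point for irPD, which is the nadir in 14.8.2 and the baseline in 14.8.5. That is a separate inconsistency and does not alter the sign problem.

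The cost is the correction of one appendix table, and of any worksheet or program already copied from it. Sample size, visits and the RECIST v1.1 analyses do not change.
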